3.3 RECRUITMENT AND RETENTION STRATEGIES

3.3.1 RECRUITMENT STRATEGY

Subjects will be recruited through (1) syringe services programs (including the Downtown Needle Exchange at Robert Clewis Center) (2) opioid treatment and behavioral health programs (including Evergreen Treatment Services) (3) community-based agencies that serve persons who inject drugs living with HCV (including the Hepatitis Education Project), and (4) low-income housing sites/homeless shelters. We will also recruit participants from the Phase 1 qualitative study who gave permission to be contacted in the future to participate in this new study.

The uncertainty of the COVID-19 response's impact has led us to develop multiple recruitment plans:

1. Research staff may receive referrals to the study from personnel who interact with potential subjects at these sites.
2. Potential participants may self-refer to the study by contacting Research staff directly using information on public recruitment materials.
3. If research staff are able to go to sites listed above for recruitment, they will approach potential subjects directly.

We will primarily rely on staff at the community sites listed above to make referrals to study staff members and will keep signage and flyers on-site at these locations with our recruitment times at a given site. When appropriate, we may directly approach potential participants at these sites. Prior to conducting eligibility screening visits in person at these agencies, staff will identify a physical space at a given agency that will allow staff to maintain confidentiality.

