3.4.2 EVERGREEN TREATMENT SERVICES/ DOWNTOWN EMERGENCY SERVICE CENTER

Evergreen Treatment Services (ETS) is an opioid treatment program organization with three locations in the Puget Sound region. Study recruitment will be focused at the Seattle Clinic site where ETS patient attend medical provider appointments, counseling services, and receive their medications for opioid use disorder (MOUD). ETS medical providers and counselors can refer their patients for HCV treatment to the Community Pharmacists and Patient Navigator when both are located at the ETS Seattle Clinic one morning a week, or directly to the Kelley-Ross pharmacy/HEP locations. Community Pharmacists and Patient Navigator will be onsite at the Seattle Clinic on Thursdays mornings 9am-12pm, as of 03/04/2021.

Downtown Emergency Service Center (DESC) provides supportive housing, case management, substance use disorder treatment, and medical services at 12 locations throughout Seattle and several other adjacent cities. DESC providers at several locations are able to refer clients interested to HCV care to the Community Pharmacists for treatment. However, given the limited space available at DESC locations, DESC clients who are interested in participating in the study would need to travel to HEP so that research staff could screen for eligibility and complete consent procedures.

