4.3.1 ASSESSMENTS OVERVIEW

The baseline survey will assess socio-demographics, substance use*, HIV risk behaviors*, and awareness of and interest in HCV treatment. After 6 months, participants will complete a follow-up (final) survey which will include information on:

- a) Whether an evaluation for HCV occurred at the community pharmacy or another site since the baseline visit
- b) Whether HCV treatment was initiated since baseline visit— assessed by self-report and pharmacy/medical records for confirmation.
- c) For patients who report that they have not been treated for HCV, reasons why (co-morbid conditions interfering, competing priorities, lack of interest, spontaneous clearance, etc.).
- d) Substance use*—measured by the modified Addiction Severity Index (ASI)(28)
- e) HIV Risk Behaviors*—measured by the modified HIV Risk Behaviors Survey (RBS)(29, 30)
- f) Receipt of naloxone, PrEP, and medications for OUD: self-report, confirmed with review of pharmacy record of dispensation/refills.
- g) Medication satisfaction, tailored to direct-acting antiviral treatment
- h) Medication adherence— assessed by record of medication pick-ups and also through self-report
- i) Injecting network (number of partners they have shared injected drugs with and, of those, how many they would be willing to refer to the site where they were treated)
- j) Completion of HCV Treatment – self-report and medical record chart review to assess if HCV treatment was fully completed.
- k) Sustain Virologic Response (SVR12) – Medical record review to assess obtainment of SVR12 results among participants who complete HCV treatment. For patients missing SVR12 results at the time of 6 month follow-up (either due to not yet having reached 12 post-treatment date or simply missing data), chart reviews will be conducted again up to 3 months after the 6 month follow-up.

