6 STATISTICAL ANALYSES

This study will provide estimates of what proportion of HCV-infected PWID successfully link to and utilize the community-pharmacy model.

The primary feasibility/acceptability outcome will be the proportion (and 95% confidence intervals) of participants who are evaluated for HCV treatment in the community-pharmacy program. Secondarily, we will evaluate HCV treatment outcomes (initiation, completion, and SVR12/cure), medication adherence, substance use, HIV risk

behaviors, and receipt of other medications (naloxone, PrEP, and medications for OUD). Finally, we will assess treatment satisfaction and willingness to refer an injecting partner to the community pharmacy for treatment.

Given our estimated sample size of 40 we can provide a range of estimates and 95% confidence intervals (CIs) for the following hypothetical scenarios: Using binomial “exact” calculation to estimate CIs, if we assume 0.5 of the sample (i.e., 20/40 participants) achieves the outcome, the estimated 95% CI is 0.34 to 0.66. If 10/40 achieves the outcome (0.25), the estimated 95% CI is 0.13-0.41; if 30/40 achieves the outcome (0.75) the estimated 95% CI is 0.59-0.87.

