General Information

Primary Researcher(s):	[name], [name], [name], [name]
Collaborators:	[name], [name]
Project Title:	Evaluation of a community-pharmacy program for medications to treat and prevent HCV, opioid use disorders, overdose, and HIV among HCV-infected PWID.
Date:	July 11, 2022

Study Aims and Design

General Context / Purpose: *A general context for the study and the particular contributions of the project*

The opioid epidemic is a major public health crisis in the United States, leading to substantial morbidity and mortality related to the consequences of opioid use disorders and injection drug use, namely hepatitis C virus (HCV), HIV, and overdose. Yet, we are at a unique historical moment, as we possess effective medications that can improve and sustain the lives of people who inject drugs (PWID). Currently there are medications that can be prescribed to 1) cure HCV (directly-acting antivirals or DAAs), 2) prevent HIV infection (Pre-exposure Prophylaxis [PrEP]), and 3) treat/prevent overdose (naloxone and medications to treat OUD). Furthermore, there is an unprecedented opportunity to eliminate HCV, a disease that is transmitted through injecting drugs. However, achieving the goals of elimination will require better systems for allowing PWID access to medications to cure hepatitis C, as well as medications to prevent overdose and HIV. Pharmacists and community-pharmacy programs may be an innovative solution for this problem. Collaborative Drug Therapy Agreements (CDTAs) allow pharmacists to have authority to autonomously perform testing and prescribing and dispensing medications.

Aim(s): *The objective(s) of the analysis*

Aim 1: To conduct qualitative interviews with HCV-infected PWID to inform the development of a community-pharmacy program to expand access to medications to treat and prevent HCV, opioid use disorders, overdose, and HIV.

Aim 2: To pilot and evaluate a community-pharmacy program for medications to treat and prevent HCV, opioid use disorders, overdose, and HIV among HCV-infected PWID.

We will examine the following sub-aims:

1. The number/percent of participants who successfully link to the community pharmacy program and are seen for initial evaluation.

2. The number/percent who initiate medications for HCV.
3. Number/percent who receive other medications (naloxone, PrEP, and MOUD)

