M6hcvothproccure	Has your provider told you that you are cured of hepatitis C?	Yes/no	9
m6hcvpharmdsrv12res ult	What were the results of that test?	Categorical	9
ehrlabavailable (EHR)	Are there post treatment HCV viral load lab results?	Yes/no	9
ehrlabresultdetect, ehrlabresultdetect2 (EHR)	Result (undetectable, detectable & quantifiable, detectable & unquantifiable)	Categorical	9

Descriptive/Other Variables of Interest (Baseline variables listed, 6-month follow-up variables start with "m6...":

Variable Name	Definition	Variable type	Sub-aim #
age	Age	continuous	NA
race	race	Categorical, nominal	NA

hispanic	Ethnicity/Hispanic/latinx	Yes/no	NA
gendid	Gender identity	Categorical, nominal	NA
Shstay	In the past 90 days, or since [des_neg90daycalc_2], where have you typically spent the night? *read options to participant, check all that apply	Discrete, check all that apply	NA
Shemploy	How would you describe your current employment status?	Categorical, nominal	NA
shinsur	Do you currently have health insurance or health care coverage?	Yes/no	NA
shinsurtype	What kind of health insurance or coverage do you currently have?	Categorical, nominal	NA
txsought	Prior to participating in this study, have you ever sought treatment for hepatitis C?	Yes/no	NA
othrxhivpos	have ever been told that you are HIV-positive?	Yes/no	NA
othrxnalox	Do you currently have Naloxone (i.e. Narcan), a medication to treat an overdose? It can be either on you right now, or at the place where you stay.	Yes/no	3
othrxoudrx	In the past 12 months, since [des_neg1yearcalc], which of these medications have you been prescribed and used as directed?	Categorical, nominal	3
Othrprepuse, or othrxprepnnow	Have you ever used PrEP? Or taking now?	Yes/no	3
*asi...	Variables for ASI substance use and injection drug use	ASI past 30 days Route Number of days	4
hivdayshare	How many times did you use a cooker/cotton/rinse water that had been used by another person who injects in the last 30 days?	Discrete, count between 0-30	5
hivshareafter	How many times did you share your works (needle/syringes) with somebody else after you used it in the last 30 days?	Discrete, count between 0-30	5
Hivinsertvagcond Hivinsertanalcond Hivreceptvagcond hivreceptanalcond	Episodes of sex without condom	Discrete, count between 0-30	6
M6pnexpplan	My navigator and I developed a plan for hepatitis C treatment.	Categorical, ordinal	7
M6pnexpunderstand	My navigator and I understand each other.	Categorical, ordinal	7

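### Sub-aim 3 is receipt of naloxone, PrEP and MOUD, but the SAP maps it only to self-reported possession or past use, with no since-baseline window and no dispensing-record variable

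*SAP*

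**What the plan says.** The SAP (Study Aims and Design) gives sub-aim 3 as "Number/percent who receive other medications (naloxone, PrEP, and MOUD", under an aim to pilot and evaluate the pharmacy program. Protocol section 6 lists "receipt of other medications (naloxone, PrEP, and medications for OUD" among the secondary evaluations. Protocol 4.3.1 item f, in the list for the 6-month survey, says how receipt is established: "Receipt of naloxone, PrEP, and medications for OUD: self-report, confirmed with review of pharmacy record of dispensation/refills".

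The SAP table of descriptive and other variables maps three entries to sub-aim 3:

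- Naloxone (`othrxnalox`): "Do you currently have Naloxone (i.e. Narcan), a medication to treat an overdose", with the added instruction "It can be either on you right now, or at the place where you stay".
- MOUD (`othrxoudrx`): medications prescribed and used as directed over the past 12 months.
- PrEP: ever used, or taking now.

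The heading of that table says "Baseline variables listed, 6-month follow-up variables start with" an m6 prefix. The follow-up versions of these three items are therefore implied, but their wording is not given.

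The Analytic Plan compares OUD and PrEP medications between baseline and final visit in Table 2, using McNemar's exact test or a t-test. Its text does not name naloxone.

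**The concern.** The endpoint is an event in a period: a medication was supplied after the person joined the study. The listed variables describe a state on the interview day (naloxone), use over a year (MOUD), or lifetime or current use (PrEP). A state is a poor stand-in for an event when people may enter already in that state and may leave it after the event.

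Both can happen here. Protocol 3.3.1 states "Subjects will be recruited through (1) syringe services programs", then opioid treatment programs. Protocol 3.4.2 describes a clinic where patients "receive their medications for opioid use disorder (MOUD". Protocol 1.2 says the partner pharmacy itself has run take-home naloxone since 2012, so even a kit from that pharmacy may predate enrolment. In the other direction, a kit that has been used or passed on has served its purpose, but the possession item reads no.

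At stake is whether the sub-aim 3 percentages can say anything about what the program delivered beyond HCV treatment.

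**Working it through.** **1. Endpoint against variable.**

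| | Receipt under item f | SAP variable for sub-aim 3 | Since-baseline window | Source asked | Dispensing field |
|---|---|---|---|---|---|
| Naloxone | self-report plus pharmacy record | has it now | no | no | none |
| MOUD | same | past 12 months | no | no | none |
| PrEP | same | ever, or now | no | no | none |

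**2. The SAP does this for HCV drugs.** Several follow-up items on HCV care ask about the period since the first visit and name the pharmacist. Record-based fields capture pick-up (`ehrrxreceived`) and dispensing dates (`ehrrx1disptime` and its successors). Nothing equivalent is mapped to sub-aim 3, so the confirmation step of item f is not carried into the SAP.

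**3. What the paired comparison recovers, if the follow-up items mirror the baseline ones.**

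- *MOUD.* At month 6 a 12-month look-back covers months −6 to +6, so 6/12 = half of it precedes enrolment. The baseline item covers months −12 to 0. Use in months −6 to 0 falls in both windows and reads yes at both visits. A change from no to yes is therefore a start after enrolment. Pairing recovers new starts; the plain month-6 percentage does not.
- *PrEP.* A change from no to yes on ever-use is likewise new. A current-use item misses anyone who started and stopped between visits.
- *Naloxone.* A change from no to yes would show a kit acquired from some source. It misses kits received and gone, and new kits given to people who already had one. The Table 2 text does not name naloxone in any case.

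**4. The plan's own precision figures.** Protocol section 6 gives exact binomial intervals for n = 40. The lower limit is the 0.025 quantile of Beta(x, n−x+1); the upper limit is the 0.975 quantile of Beta(x+1, n−x). Results: 10/40, 0.127–0.412; 20/40, 0.338–0.662; 30/40, 0.588–0.873. All match the stated values after rounding.

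**5. How far possession can drift from receipt (naloxone).** The documents give no baseline possession, retention or use-up rates, so every input below is assumed. Let r be the share who receive naloxone from the program during the study, b the share holding a kit at baseline, k the share of those holders (among non-recipients) who still have it at month 6, and u the share of recipients with none left. Assume that receipt is independent of baseline possession, that nobody acquires a kit elsewhere, and that the month-6 item is worded as listed. Then

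item reads yes = r(1−u) + (1−r)·b·k.

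With r = 0.25 (true receipt 10/40):

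| b | k | u | Calculation | Expected reading | Exact 95% CI |
|---|---|---|---|---|---|
| 0 | – | 0.5 | 0.25×0.5 | 5/40 | 0.04–0.27 |
| 0.25 | 0.5 | 0.25 | 0.1875 + 0.09375 | 11.25/40 | – |
| 0.5 | 1 | 0 | 0.25 + 0.375 | 25/40 | 0.46–0.77 |
| 0.75 | 1 | 0 | 0.25 + 0.5625 | 32.5/40 | – |

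Over b from 0 to 0.75, k from 0.5 to 1 and u from 0 to 0.5, the reading runs from 5 to 32.5 of 40. The errors can also nearly cancel, as in the second row. The interval around 25/40 excludes 0.25; the interval around 5/40 just includes it.

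**The case against.** The strongest reply is that the listed items are baseline items. A baseline question cannot ask about receipt during the study, several follow-up HCV items that are shown do use a since-first-visit window, and Protocol section 2 says the follow-up survey covers receipt of naloxone and PrEP. The SAP gives no scoring rule that turns possession into receipt, and sub-aim 3 neither says during the study nor restricts the source. This stands in part: the misclassification is conditional on the unseen wording. It does not remove the gap, because the SAP shows no receipt item and no dispensing field for this sub-aim.

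The data variable table in Protocol 4.3.1.1 also lacks a naloxone row and marks record review only for HCV treatment completion and SVR12. That is weak evidence. The table also leaves out record checks on treatment initiation and adherence that 4.3.1 requires, and the SAP has record fields for both.

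Three stronger inferences are tempting, and the documents do not support them:

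- *The percentages will mainly reflect what recruitment sites already supply.* For naloxone, no section says those sites distribute it, and Protocol 1.2 speaks of major gaps in access.
- *Receipt will be overstated several-fold.* Suppose 24/40 hold kits throughout, 10 of the other 16 receive one and 3 of those 10 have none left. The item reads (24+10−3)/40 = 31/40. Against 10/40 the ratio is 3.1, but only if no baseline holder receives a pharmacy kit. If they do at the same 10/16 rate, 24×10/16 = 15 more receive one, true receipt is 25/40, and the ratio is 31/25 = 1.24.
- *Opioid treatment clinic patients count as MOUD receivers whatever the pharmacy does.* That could apply only to a raw month-6 percentage. In McNemar's test, patients on MOUD at both visits are concordant pairs and contribute nothing.

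**Conclusion.** Wrong as written. Sub-aim 3 is receipt, Protocol item f defines receipt with dispensing-record confirmation, and the SAP supplies only self-reported possession or past use, with no since-baseline window and no dispensing variable. Naloxone is affected most, because the comparison text does not name it. For MOUD and PrEP the paired comparison limits the damage, but the plain percentage that sub-aim 3 asks for remains exposed.

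Reading sub-aim 3 as receipt during the study rests on the evaluation aim and on Protocol sections 2 and 4.3.1, since the SAP sentence itself gives no period. The misclassification also assumes that the follow-up items repeat the baseline wording. Its size and direction cannot be computed from the documents. The assumed ranges show only that it can go either way and can exceed the sampling error. This is a secondary descriptive outcome in a 40-person pilot; the primary outcome, evaluation at the pharmacy, is untouched.

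**What to change.** - **Naloxone and PrEP.** Add a SAP variable for any dispensing between baseline and month 6, with date, from the Kelley-Ross record that item f already requires. State the follow-up self-report item with a since-baseline window and the source of supply, so that kits or prescriptions from elsewhere are counted and distinguishable. Report receipt split by possession or use at baseline.
- **MOUD.** Report new starts among participants not on MOUD at baseline. Use dated self-report where pharmacy records do not reach: Protocol 4.2.1.1.2 names release forms only for the Hepatitis Education Project and Kelley-Ross, so treatment from outside programs may not be on file.
- **Possession.** Keep current naloxone possession at both visits as a descriptive row, labelled as possession, and name it in the Table 2 text.

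The cost is a few extraction fields and SAP wording. The Kelley-Ross release is signed at enrolment, and the eligibility script (Protocol 8.2.1) already tells participants that records on these medications will be reviewed. If follow-up interviews are already complete, the self-report wording can no longer change, but the dispensing field can still be extracted. The downside is that the reported percentages are likely to be smaller and rest on fewer people.

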4. Baseline and 6-month follow-up substance use in past 30 days via modified Addiction Severity Index (ASI)
5. Baseline and 6-month follow-up the number of injecting episodes using shared needle/syringe within the past 30 days via the modified Risk Behaviors Survey (RBS)
6. Baseline and 6-month follow-up the number of episodes of unprotected vaginal or anal sex within the past 30 days via RBS
7. Self-reported participant Likert scale surveys of satisfaction and willingness to refer an injecting partner to the community pharmacy for treatment
8. The number/percent who complete treatment for HCV, defined as having received all planned medication doses.
9. SVR12 defined as undetectable HCV viral load at least 12-weeks post treatment completion

NOTE: This analysis plan does not include the data on injection network

Inclusion/Exclusion Criteria: *Defines the population to be analyzed. Describe criteria that were part of original data collection and additional criteria needed for this particular project.*

Inclusion criteria:

1. Age ≥ 18 years old
2. Injected any drug within the past 90 days (intravenous or intramuscular)
3. Tested positive for HCV (screening and/or confirmatory viral load) at a community testing site (syringe exchange programs, addiction treatment programs, homeless shelters, urban drop-in shelters and low-income housing sites)
4. HCV treatment naïve and not currently already receiving treatment
5. Willing to undergo evaluation for HCV at a community pharmacy

Exclusion criteria:

1. People who plan to leave the Seattle area within 6 months
2. Do not wish to be treated for their HCV infection
3. Are known to be pregnant
4. Report impending incarceration that would disrupt clinical care
5. Are not comfortable reading and speaking English
6. Report being HIV-positive
7. Report having end-stage renal disease or require dialysis treatments
8. Report prior enrolled in (i.e. completed at least the initial intake appointment) the Kelley-Ross pharmacy program for hepatitis C treatment ("One Step Hep C Free")

Data and Variables Needed for Analysis

Add rows to tables as needed

If a dataset or variable needs to be created / does not exist yet, you can note that here.

Variable Name	Definition	Variable type	Sub-aim #
m6hcvtxpharmd	Since our first visit, were you seen by the pharmacist (refer to them by name) for hepatitis C medications?	Yes/no	1

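### SAP sub-aim 5 is labelled as needle/syringe sharing, but no variable listed for it covers injecting with a needle or syringe that someone else had used

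*SAP*

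**What the plan says.** In the SAP's list of sub-aims under Aim 2, sub-aim 5 is "the number of injecting episodes using shared needle/syringe within the past 30 days via the modified Risk Behaviors Survey (RBS"), measured at baseline and 6 months. Sub-aim 6 is its sexual-risk counterpart: "the number of episodes of unprotected vaginal or anal sex within the past 30 days via RBS".

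The table of descriptive and other variables tags two rows to sub-aim 5:

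- `hivdayshare`: "How many times did you use a cooker/cotton/rinse water that had been used by another person who injects in the last 30 days"
- `hivshareafter`: "How many times did you share your works (needle/syringes) with somebody else after you used it in the last 30 days"

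Both are typed "Discrete, count between 0-30". The four condom variables for sub-aim 6 have the same type.

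The SAP's instructions for its variable tables say "Add rows to tables as needed" and "If a dataset or variable needs to be created / does not exist yet, you can note that here". A line below the sub-aims adds "NOTE: This analysis plan does not include the data on injection network".

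Protocol section 4.3.1 names the modified Risk Behaviors Survey (RBS) as the instrument, and table 4.3.1.1 schedules it at both visits. Its items are not reproduced. Protocol section 6 places HIV risk behaviours among the secondary outcomes. The SAP's Analytic Plan compares them between baseline and final visit in its Table 2.

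**The concern.** The label and the listed contents of sub-aim 5 do not match. A reader of the results would take a figure for injecting episodes with a shared needle or syringe to mean that the participant injected with someone else's used needle. Neither listed item counts that.

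Two kinds of wrong statement could follow. Receptive needle use could rise or fall over six months while both items stay flat, and the report would show no change in needle sharing. Conversely, a change in the sharing of cookers, cotton or rinse water could be reported as a change in needle sharing. These are different behaviours, and passing on a used needle concerns risk to the other person and not to the participant.

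There is a smaller question about the response range. The sub-aim 5 items ask for a number of times and the sub-aim 6 variables count episodes, yet all have a range that equals the number of days in the recall window.

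**Working it through.** No stated figure in the plan bears on this point, so the check sets the passages side by side.

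**Step 1. Place the two items by object and direction.** The four-way layout is mine and serves only to order the items.

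| | Received from another person | Passed on to another person |
|---|---|---|
| Needle/syringe | no listed variable | `hivshareafter` |
| Cooker, cotton, rinse water | `hivdayshare` | no listed variable |

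The two items fill 2 of 4 cells. The cell closest to the sub-aim's wording, needle or syringe received, has 0 listed variables.

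**Step 2. Count coverage under each reading of the sub-aim.** The SAP does not define sharing.

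- Narrow reading (the participant's own injections with a used needle or syringe): 0 of 2 items count it.
- Broad reading (any needle or syringe sharing, either direction): 1 of 2 items covers part of it, namely `hivshareafter`.

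Under both readings `hivdayshare` lies outside the label and receptive needle use is not measured by any listed variable.

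**Step 3. Look for the item elsewhere in the SAP.**

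- The Addiction Severity Index (ASI) block is one shorthand row tagged to sub-aim 4. It gives route and number of days and names no sharing item.
- The injecting-network data are excluded by the SAP's own note. As protocol section 4.3.1 describes them, they count partners, not injecting episodes.
- No added row, and no note of a variable still to be created, appears for sub-aim 5, although the table's instructions invite both.

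**Step 4. The 0-30 range.** Six variables have this type: 2 for sub-aim 5 and 4 for sub-aim 6. If the unit is times, the top of the range is 30 / 30 days = 1 a day on average. A participant with 2 events a day would have 2 x 30 = 60, which does not fit. The rate of 2 a day is an assumption for illustration; the documents give no rates. If the unit is days, 0-30 is the full natural range, but the variable is then not the number of episodes named in the sub-aims. The SAP states no rule for values above 30.

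**The case against.** The strongest reply is that this may be an omission from a table and not from the data. Sub-aim 5 says its data come from the modified RBS, that survey is given at both visits, and its form is not in the documents. The SAP table also uses shorthand elsewhere, as the single ASI row shows. This stands as a limit. A reader might infer that the study never asked about injecting with used needles, and the documents do not support that. They show only that no such variable is listed. The reply does not remove the mismatch, because an analyst who follows the table as written would build the outcome from the two listed items.

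Second, `hivshareafter` does concern needles and syringes, so the outcome is partly covered. That is correct for the giving direction.

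Third, the wording does state a unit, times or episodes, and the 0-30 range may be a loose description or an entry limit. This also stands. A reader might infer that counts were cut off at 30, or that the variables are really days because one variable name contains that word. No truncation rule is stated, one name out of six is thin evidence, and the SAP's Table 2 layout, which might settle the unit, cannot be seen. The range needs clarifying and is not a demonstrated error.

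Fourth, it is tempting to argue that the omitted behaviour is the one the programme targets, citing the navigator steps in protocol appendix 8.4. Those steps advise against sharing any injection supplies, come after treatment, and do not single out receptive needle use. They cannot carry that argument.

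Finally, the stakes are modest: this is a single-arm pilot of 40 with a feasibility primary outcome, and no decision rule or sample-size figure depends on sub-aim 5.

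**Conclusion.** The mismatch holds on the face of the SAP. Of the two variables mapped to sub-aim 5, one measures equipment sharing and the other measures needle/syringe sharing in the giving direction only. None covers injecting with a needle or syringe that someone else had used. This is more than missing detail, because following the table would produce a result whose label does not describe its contents.

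The effect is confined to a secondary outcome, and the primary outcome, evaluation in the pharmacy programme, is untouched. The size of any distortion cannot be given because the documents contain no sharing counts. The conclusion assumes that the SAP table is what the analyst will use and that sub-aim 5 is at least meant to include the participant's own use of used needles. It does not assume that the survey lacks the item. The 0-30 range is a minor clarification alongside this.

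**What to change.** Check the modified RBS form first.

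1. **If it holds an item on injecting with a needle or syringe that someone else had used:** add that variable to the SAP table as the sub-aim 5 row, and report equipment sharing separately from it.
2. **If it does not:** rename the outcome to what the two items measure, report use of others' equipment and passing on of used needles/syringes as two separate results, and make no claim about injecting with needles others had used. Record this as a change to the stated outcome, with its date and reason.
3. **Minor clarification:** for each of the six variables typed 0-30, reconcile the range with the wording by stating whether the value is times (or episodes) or days. If entries were limited to 30, report how many participants are at 30 at each visit.

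The first route costs one table row. The second costs a documented change to a secondary outcome and leaves it less direct than sub-aim 5 now states; a missing item cannot be recovered for visits already completed. The third costs a line of text and, if a limit applied, one count per visit for each variable.
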